2.4.2.4 Minimum detectable effect size given the sample size at analysis stage

With the sample size at the final data collection point (i.e. post-attrition, n = 4,200), we present the minimum effects we are powered (at 80% level) to detect for six primary outcomes among the trial participants in Table 7, which also provides corresponding benchmarks to interpret those effect sizes.

Table 7. Minimum detectable effect size for primary outcomes given a post-attrition sample size of 4,200

Prima	ry outcomes	MDES	MDES as % of min. (or max.) recommended intake
PA	Daily MVPA (min/day)	2.4 min/day	~ 10% (150 min/week, according to the UK CMO's Physical Activity Guidelines)
	Daily steps	371 steps/day	~ 4% (8,000 steps/day, according to the UK CMO's Physical Activity Guidelines)
Diet	Fruit and vegetables (g/day)	18.7 g/day	~ 5% (~ a quarter of a F&V portion)
	Fibre (g/day)	0.74 g/day	~ 2.5% (~ a third of an apple)
	Free sugars (% food energy)	0.63%	~ 13% of the upper limit of % food energy intake (≤5% food energy)
	Saturated Fat (% food energy)	0.31%	~ 2.8% of the upper limit of % food energy intake (≤11% food energy)

2.5 Assignment of interventions

2.5.1 Allocation

To collect comparable baseline data between trial arms, all participants will be able to order a free wearable device if they do not own one, install the pilot app, and initially have access to only the control group version of the app. After baseline data is collected, users will be randomly assigned to one of the four trial arms. Those in the intervention arms would gain access to the incentives and other app features; those in the control arm would have access to the app features but not be rewarded with incentives. All individuals in the same household will be allocated to the same trial arm.⁴⁸

At the analysis stage (end of the trial), we aim at having 3 users in the control group for each user in the treatment arms. However, we expect attrition to differ across control and treatment groups, as shown in Table 6.

⁴⁸ Please note that this does not mean that we are aiming at recruiting a minimum number of households, or that some households will be excluded from the trial, and it won't be a requirement that all household members sign up. This simply means that whenever more than one user belonging to the same household sign up, they will all be allocated to the same trial arm.

Based on these attrition estimates, Table 8 shows the optimal allocation of users to trial arms at randomisation.

Group	E	stimates
	N at the end of the baseline period (at randomisation)	Allocation ratio
1. High incentive	~1,900	12%
2. Medium incentive	~1,950	12%
3. Low incentive	~2,250	15%
4. Control group	~9,400	61%

Table 8. Optimal allocation of users to trial arms at randomisation

2.5.2 Blinding (masking)

Participants will be aware they are participating in a randomised controlled study, as they will be asked to provide consent. However, we expect that users will not be able to figure out to which treatment arm they are assigned to (low, medium or high level of incentive) based on the information available on the app and their user journey, whilst it is likely that users in the control group will be able to correctly identify that they have been assigned to the control trial arm (no incentive).

While is not possible to deliver a fully blind design for trial analysts given the differences that will be identifiable in the data at the point of analysis, datasets for each arm will be labelled neutrally (e.g. A, B, C and D instead of treatment, control).

2.6 Data collection, management, and analysis

Attrition from the trial (users dropping off from data collection) is the largest threat to the success of the evaluation and knowing whether a financial incentive scheme is effective within this context.

The next section elaborates in details the data collection methods, including:

- How to collect data and time points of data collection;
- How we plan to adjust for differential attrition across trial arms;
- How to mitigate the risk of differential attrition.

2.6.1 Data collection methods

2.6.1.1 Assessment and collection of data

Physical activity outcomes. The PA measures will be automatically recorded through the wearable device for the full duration of the pilot, but it requires users to sync their device with the app for HUL to collect this data. Users will be reminded to wear and sync the device during crucial data collection weeks/moments. Participants will be nudged (via push notifications) to wear and synchronise the wearable device during the trial period to improve accuracy of data collection.

Dietary outcomes⁴⁹**.** Diet will be measured using Intake24, a retrospective 24 hour dietary recall questionnaire.⁵⁰ Completing this questionnaire can take up to 20 minutes. We follow the approach taken by the The Scottish Health Survey and encourage two recalls at each data collection point.⁵¹ Users may provide a recall for a weekday or a weekend day, based on when they complete the questionnaire.⁵²

Measurement time points across the pilot. Figure 3 also provides a high-level user journey for participants, from an evaluation point of view, to illustrate when users are asked to provide data throughout the trial. Broadly speaking, as illustrated in Table 9, we envisage 4 data collection points during the study:

- the baseline period;
- the 5th week after randomisation for the 1m mark;
- the 13th week after randomisation for the 3m mark;
- the 21st week after randomisation for the 5m mark.

Additional measurement time point at the 12m mark. In addition to the 4 data collection points, we might add another time point at the 12m mark if the pilot programme is extended by DHSC. If the extension takes place, an updated evaluation plan and ethics approval will be sought before data collection. This extension would be subject to contractual agreement.

⁴⁹ In Appendix B we set out the other options for measuring diets that we considered and the rationale that led us to select Intake24 over other alternatives.

⁵⁰ In using Intake24 questionnaire, we will strike a balance between maximising the validity and reliability of the method (Intake24 is used for the National Diet and Nutrition Survey) whilst minimising the burden on participants (more robust measures of dietary intakes, such as food diaries would be much more time-consuming). Based on previous studies, the user experience of completing Intake24 is generally positive. Feedback from participants in the field test of Intake24 suggests that the majority of people found the system user-friendly, enjoyable to use, and felt it accurately captured their diet. ⁵¹ It is our assessment that two recalls is a reasonable mid-point between the single administration recommended by the National Cancer Institute and the four recalls used by PHE's NDNS and in the original validation study. Four recalls would force us to extend the sign-up onboarding period of at least one week, with significant risks to the retention of users in the programme as it would involve asking participants to complete 80 minutes of questionnaire at each measurement time point. ⁵² The Intake24 team at Cambridge reassured BIT that it is not necessary that each user provides a recall for a weekday and one for the weekend for obtaining robust results. This is because it is only necessary that across the whole sample some users will provide some recalls for weekdays and some for weekends. As different users are nudged to provide a recall on different days, based on when they begin the onboarding phase, it is reasonable to expect that overall some recalls will reflect weekday dietary behaviour and some recalls weekend dietary behaviour.

Data collection point	Data collection method for dietary outcomes	Data collection method for PA outcomes
Baseline period	Day 1 of baseline: users are invited to provide their first recall. Users are informed that the first two recalls they will provide (to be provided on two separate days, including information about weight) will be remunerated with a payment of £5 each in points. The second intake24 is optional; users are encouraged to complete the second one within 3 days. The survey will be prominently displayed on the dashboard of the app when users open it for the full duration of the baseline period.	If a user owns a wearable device, they are encouraged to sync their own device with the app and provide their PA data from the first day of the baseline period. If a user orders a wearable device, they are encouraged to sync it with the app and provide their PA data as soon as they receive the device. Users will be nudged for the full duration of their baseline period to wear the device and periodically sync it with the app. In the analysis, we will use all valid daily PA data provided during the baseline period (valid = device worn for at least 6h)
1 month mark (starting the 5th week after randomisation)	 Day 1: users are invited to provide a recall. Users are informed that the first two recalls they provide in the following two weeks will be remunerated with a payment of £5 each in points. Reminders, feedback and survey prominence are repeated as per the baseline phase. In the analysis, we will use all recalls submitted during the 5th and 6th week after randomisation for the 1m mark. 	In the 5th week after randomisation, users will be nudged to wear the device as long as possible for 7 days and sync the device with the app. In the analysis, we will use all valid daily PA data provided during the 5th week after randomisation for the 1m mark. If there are missing values in that week, we will impute them with valid values (if available) on the same day of the week within 2 adjacent weeks (i.e. weeks 3-7).
3 months mark (starting the 13th week after randomisation)	This will work as at the 1 month mark. In the analysis, we will use all recalls submitted during the 13th and 14th week after randomisation for the 3m mark. If the 'delay' and 'higher incentive' mitigation strategies are triggered: Day 1: users are invited to provide a recall. Users are informed that	In the 13th week after randomisation, users will be nudged to wear the device as long as possible for 7 days and sync the device with the app. In the analysis, we will use all valid daily PA data provided during the 13 th week after randomisation for the 3m mark. If there are missing values in that week, we'll replace them

Table 9. Data collection points and methods

	the first two recalls they provide in the following three weeks will be remunerated with a payment of £10 each. Reminders, feedback and survey prominence are repeated as per the baseline phase. In the analysis, we will use all recalls submitted during the 13th, 14th and 15th week after randomisation for the 3m mark (days 90 to 111 post randomisation).	with valid values (if available) on the same day of the week within 2 adjacent weeks (i.e. weeks 11-15). If the mitigation strategies are triggered: In the analysis, we will use all valid daily PA data provided during the 13 th , 14 th and 15 th weeks after randomisation for the 3m mark. If there are missing values in that week, we'll replace them with valid values (if available) on the same day of the week within 2 adjacent weeks (i.e. weeks 11-17).
5 month mark (starting the 20th week after randomisation)	This will work as at the 1 month mark. In the analysis, we will use all recalls submitted during the 21st and 22nd week after randomisation for the 5m mark. If the 'delay' and 'higher incentive' mitigation strategies are triggered: This will work as at the 3 month mark. In the analysis, we will use all recalls submitted during the 20 th , 21st and 22 nd weeks after randomisation for the 5m mark.	In the 21st week after randomisation, users will be nudged to wear the device for as long as possible for 7 days and sync the device with the app. In the analysis, we will use all valid daily PA data provided during the 21st week after randomisation for the 5m mark. If there are missing values in that week, we'll replace them with valid values (if available) on the same day of the week within 2 adjacent weeks (i.e. weeks 19-23). If the mitigation strategies are triggered: In the analysis, we will use all valid daily PA data provided during the 20 th , 21 st and 22 nd weeks after randomisation for the 3m mark. If there are missing values in that week, we'll replace them with valid values (if available) on the same day of the week within 2 adjacent weeks (i.e. weeks 18-24).

Data fields to be collected. The data collection will be executed by HUL and then transferred securely and anonymously to BIT. Table 10 illustrates the structure of the data fields to be collected by HUL and to be transferred to BIT. See **BIT data list for impact** evaluation - V5 for the complete list of data fields.

General area	Specific area	Data Field	Mandatory	Usage	Unit and reasonable range
Meta data,	System	Anonymised GUID	Yes	For joining various datasets	Multi digits
including	Household	Household ID	Yes	For analysis	N/A
inclusion & exclusion	Eligibility	Download and install app	No (auto collected)	To select eligible participants	Yes; No
criteria	Eligibility	Consent to participate	Yes	To select eligible participants	Yes; No
	Eligibility	Consent date	Yes	To select eligible participants	Within the recruitment window. If a user does not consent, the consent date will be encoded as 0000-00-00 and the user cannot proceed to health condition and address pages.
	Eligibility	Health condition	Yes	To select eligible participants	Suitable; unsuitable
	Eligibility	Adult status	No (derived from age)	To select eligible participants	Adult; Minor
	Eligibility	Full postcode	Yes	To select eligible participants, and to merge postcode-level deprivation data with GUIDs	N/A
	Eligibility	Resident of Wolverhampton	Yes	To select eligible participants	Yes; No
Uptake and	Wearable use	Daily wear time	Yes	For imputation of missing values	0~24 hours
Engagement	App use	Whether a GUID opens the app by day	Yes	To infer active user status and attrition	Used to identify different types of users: Very active users: app installed and opened at least once over the course of 7 days Active users (Users who have opened the app at least once in the last 30 days). Inactive users (Users who have not opened the app in 30 days)

Table 10. Illustrative structure of data fields to be collected by HUL and to be transferred to BIT

			Churn outs (Users who have not open the app for more than 30 days)
App open date	Yes	To examine wear time / app opens for the same GUID over time	N/A

[figure not shown]

Figure 3. High-level user journey for participants, from an evaluation point of view.

2.6.2 Data quality management

We will seek to obtain high-quality **physical activity data** with two strategies:

- **During data collection.** Participants will be nudged to wear and synchronise the device throughout the trial period to maximise the data fidelity of MVPA mins and steps count and to minimise missingness.
- **Before analysis.** Based on univariate analysis, we will search for and exclude or replace outlier values. We are aware that due to some technical glitches, participants' physical activity data may exceed plausible boundaries (e.g. more than 1440 minutes of MVPA per day, or more than 3 million steps per day). To mitigate the influence of those outliers, we will exclude the implausible records and apply further boundary rules (excluding observations that are below the 2.5th or above the 97.5th percentiles) to ensure data fidelity. BIT will also inspect PA sample data after trial launch and refine the above criteria to handle outliers if necessary (see section 2.6.3.2 for details).

Likewise, the quality of **diet data** will also be managed at two stages: during data collection and before data analysis:

- **During data collection.** Intake24 includes automatic checks and nudges to rule out implausible inputs (e.g. portion size, time gap between meals).
- Before analysis.
 - (i) Firstly, we will exclude administrations satisfying any of the following conditions (these conditions were used in the National Diet and Nutrition Survey (NDNS)):
 - Fewer than 10 food items in a recall
 - 3 or fewer eating occasions in a recall (this includes occasions when a participant reports consuming only a drink without food)
 - Completion time of under 3 minutes
 - Total energy intake less than 400kcal or more than 4,000kcal and the individual had not stated that they consumed "less than usual", "more than usual", or that they were on a weight gain or weight loss diet
 - (ii) After doing this, we will inspect the distributions of the dietary outcomes and compare that against the mean level and standard deviation of UK adults' food and macro-nutrients consumption. We will then exclude values below the 1st or above the 99th percentile, by gender.

2.6.3 Statistical methods

2.6.3.1 Attrition management

Based on the previous literature and on HUL's experience, we expect high levels of attrition (See Section 2.4.2.3).

Attrition (users not providing the wearable device data or not completing Intake24) might happen for multiple reasons (e.g. lack of engagement with data collection, lack of engagement with the app, etc.) at any time. For the purpose of the impact evaluation, our core concern is attrition at the specific measurement points:

- 1 month follow-up;
- 3 month follow-up;
- 5 month follow-up.

We anticipate that differential attrition might occur as participants in the control group might be less incentivised to stay enrolled in the study compared to those in the intervention groups. If the ratio of attrition between the control arm and the pooled intervention arm is greater than or equal to 1.1 (the average relative attrition rate according to a recent meta-analysis on differential attrition of behavioural change interventions⁵³), we propose to adjust for the differential attrition using inverse probability weighting (IPW)⁵⁴, a method proven effective in reducing selection bias for longitudinal studies. The IPW works by modelling the probability of successful retention at 1 month, 3 months and 5 months using baseline observables and then re-weighting those that were retained, so that the reweighted data would be balanced in terms of baseline observables across different arms.

In practice, this means running a logistic regression to calculate the probability of successful retention as a function of baseline variables, getting the fitted probabilities, and then using the inverse of these fitted probabilities as weights in the regression model.

The degree of attrition might vary with outcome measures. As physical activity outcomes are passively captured by the wearable and require no extra burden from the users other than wearing the device and syncing it with the app, we expect the degree of attrition to be lower than for the dietary outcomes measured by Intake24, which require users to spend up to 20 minutes to complete each questionnaire. We will test for differing attrition rates separately for each type of primary outcome (we will use MVPA minutes for physical activity and fruit and vegetables for diet). If we find a ratio of attrition greater than 1.1 for a given primary outcome type, we will apply IPW for all corresponding primary and exploratory outcomes related to physical activity / diet as well.

2.6.3.2 Missing data management

Missing data might occur when a user stops providing data temporarily or permanently. We suggest two different procedures to handle missing data depending on whether participants stop providing data temporarily or permanently:

⁵³ Crutzen, R., Viechtbauer, W., Spigt, M., & Kotz, D. (2015). Differential attrition in health behaviour change trials: A systematic review and meta-analysis. *Psychology & Health*, *30*(1), 122–134. doi: 10.1080/08870446.2014.953526

⁵⁴ Schmidt, S. C. E., & Woll, A. (2017). Longitudinal drop-out and weighting against its bias. *BMC Medical Research Methodology 2017 17:1, 17*(1), 1–11. doi: 10.1186/S12874-017-0446-X

- User stops providing data **temporarily**. For example, PA data may not be available on a given date, or a user provides only one Intake24 recall at a given data collection point. In the sections below, we outline how we would approach such circumstances.
- User stops providing data **permanently** (attrition from measurement). Our general principle is that we will not attempt to replace missing values when missing outcome measures are due to attrition (i.e. a user does not provide any data after a given data collection point in the trial). We define this type of missing data as 'attrition', and we detailed our approach to deal with differential attrition in the previous section.

Physical activity outcomes

For physical activity outcomes (MVPA, steps, energy expenditure), we will get daily reads from the date of onboarding to the end of the trial. It is possible that a user does not provide data on a given day for the following reasons:

- Forgetting to wear the wearable;
- Dead battery.

Individuals may also wear the wearable device on a given day but not long enough for the reading to be sufficiently accurate. We define a 'valid' read as occurring when the individual wears their wearable device for at least 6 hours in the day. Users will not be nudged to meet this criteria, but will be nudged to wear their device as long as possible each day. In the main specification for each physical activity outcome, we use 'valid' reads for all days of the 21st week (i.e. month 5) of the trial as outcomes, and also control for 'valid' reads taken in the last 7 days of the baseline period if they exist.

Additionally, it is possible for reads based on at least 6 hours of wear-time to be erroneous due to issues with the wearable devices (point 1 below). We will replace 'invalid' reads or erroneous daily reads in the last 7 days of the baseline period and 5-month measurement week as follows:

- We will exclude reads that are below the 2.5th or above the 97.5th percentile⁵⁵ within each combination of period (baseline, 1 month, 3 months, 5 months), treatment arm (no / low / medium / high incentives) and day of the week, for reads based on at least 6 hours of wear-time. This is intended to remove erroneous extreme daily reads.
- 2. We will replace invalid daily reads in the 5-month measurement week with other reads taken by the individual on the same day of the week (e.g. Monday) and within 2 weeks before or after the evaluation week as follows:

⁵⁵ We will examine these cut-offs after inspecting the trial data and adjust them if they are inappropriate, e.g. if there is a higher proportion of extremely inactive or active people than expected, we may adjust the cut-off points to make the distribution of included observations less skewed.

- If an individual has a valid read on the same day of the week for the week before or after, we will replace the invalid read with it. If an individual has valid reads for both the week before and after, we will average these two reads.
- Otherwise, if an individual has a valid read on the same day of the week for 2 weeks before or after, we will replace the invalid read with it. If an individual has valid reads for both 2 weeks before and 2 weeks after, we will average these two reads.
- Otherwise, we will not impute.⁵⁶
- 3. We will impute reads in the last week of the baseline period (i.e. (up to) the last 7 days of the individual's baseline period) in the same way, except that we will only look at earlier reads from the baseline period as potential replacements. We will only do this if a user has at least 4 days of valid baseline data. If they do not, they will be excluded from the analysis.

When analysing the effects of incentives at 1 and 3 months (i.e. the 5th and 13th weeks respectively), we will perform a similar process.

This imputation process will increase the sample size of person-day observations for the 5-month measurement week, which increases the precision of our estimates. It will also remove (i) reads based on low wear-time which may be underestimating physical activity, as well as (ii) reads that are erroneous due to malfunctioning wearable devices. This imputation process may not fully mitigate the issue that users will be more likely to wear the device when doing more PA (likely to be affected by the treatment assignment). However, we do not think this relationship will be too strong near the 6-hour cut-off point, since historical data on HUL Delta⁵⁷ users suggests that few users (<3%) wear the wearable for less than 6 hours per day on average. Alternative imputation methods that we have considered such as multiple imputation, which takes advantage of the within-subject auto-correlation over time does not fully mitigate against this issue either.

Dietary outcomes

Dietary recalls are provided by users only at key data collection points (baseline, 1 month, 3 months, 5 months). At these data collection points, users are encouraged to provide two recalls in the same week. We do not impute dietary outcomes. If a user provides one dietary recall at a given data collection point, we will not impute the other. If a user provides zero dietary recalls at a given data collection point, we will not impute the not impute either of the recalls since this requires using information that is at least 2 months away.

⁵⁶ The following example provides further clarification. Say that an individual has an invalid read from Monday 16th May, which is at month 5, i.e. 21st week into the trial after randomisation.

[•] If they have a valid read from Monday 9th May or Monday 23rd May, we will take this as the value for Monday 16th May. If they have valid reads for both dates, we will average them.

[•] If they do not have a valid read from Monday 9th May or Monday 23rd May but do have a valid read from Monday 2nd May or Monday 30th May, we will average the available reads from these dates.

[•] If they do not have a valid read from 2nd, 9th, 23rd or 30th May, we will not impute.

⁵⁷ HUL Delta is the name of HUL's own branded wearable device.

For both the primary physical activity and dietary outcomes, we examine the sensitivity of our main findings to different assumptions about missing data (see section 2.6.3.9).

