Before the trial	Onboarding phase	Adopt a flexible onboarding period for 'slow onboarding users' if needed - ideally a user completes screening in 2 or 3 weeks (nudged to do so), but if they don't, they enter the trial (randomisation) when they have met the baseline criteria, rather than after a predetermined window of time.	HUL
		The latest calendar date that a user can complete onboarding (pass screening) is the last day of the recruitment window.	
During the trial	Recruitment	Extend the recruitment period beyond 6 weeks if necessary	HUL
During the trial (triggered at M5)	Trial period	Make data collection attractive: Consider encouraging wearing and syncing the wearable device with the app in the crucial data collection weeks at m3 and m5 with a small payment (£10), if attrition is deemed relatively too high ¹³ at the data collection point at m1 and m3.	HUL
During the trial (triggered at M3 and M5)	Trial period	Make data collection attractive: Consider encouraging filling in Intake24 at m3 and m5 with a larger payment (£10), if attrition is	HUL

¹³ We consider the attrition too high if the number of users not providing their data 10% smaller than expected at the start of the 1 month mark (see Table 6 for the expected attrition at different trial stages).

		deemed relatively too high ¹⁴ at the data collection point at m1. At m5 - for PA, users will receive £5 for syncing their fitness tracker (any amount of data > 0) during weeks 21 and 22 - up to 2 times so they can earn up to an extra £10.	
During the trial (triggered)	Trial period	Extend the data collection window from 2 to 3 weeks (21 days) at m3 and m5 for all measures (i.e. Intake24, steps, WHO5, sleep and weight)	HUL
During the trial	Trial period	Pull data collection forward. Change M5 data collection window to start earlier i.e. during the 20th week (day 134 to day 155).	HUL
After the trial	Recruitment and baseline phase	Shift the focus of the evaluation to a shorter follow-up (e.g. after 3 months of treatment instead of 5 months). If the sample size at 5m is less than 80% of the total sample size (n = 4,200) that the trial requires in order to detect a minimum effect size for primary outcomes (see Table 7 for details), we will use data from the 3m mark instead of the 5m mark in the analysis. ¹⁵	BIT

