2.6.3.5 Analytical strategy for the primary analysis

The primary outcomes for physical activity are **MVPA minutes per day and daily** steps at 5 months into the trial (week 21).

We will test for differences between the pooled treatment arms and the control arm five months after randomisation using an intention-to-treat approach and a **linear mixed model (panel regression with random effects)** appropriate for clustered data with repeated measurements, in line with methodology adopted by studies with similar designs^{58,59}. As part of the analytical strategy, we will control for the individual characteristics of age, sex, ethnicity, education, BMI at baseline, the brand of wearable.

The general equation for estimating the model is as follows:

(1)
$$y_{ijd} = \alpha + \beta Treatment_j + \gamma_d + \gamma_W week_{ijd} + \gamma_B baseline_{ijd} + \gamma_M missing. baseline_{ijd} + ... \gamma_X X_{ij} + \delta_{cj} + \delta_{pij} + u_{ijd}$$

 $\delta_{cj} \sim N(0, \sigma_c^2); \ \delta_{pij} \sim N(0, \sigma_p^2) for all i, j; \ u_{ijt} \sim N(0, \sigma_u^2) for all i, j, d$

where:

• y_{iid} is the daily MVPA minutes for participant *i* within household *j* on day *d*;

⁵⁸ Harkins, K. A., Kullgren, J. T., Bellamy, S. L., Karlawish, J., & Glanz, K. (2017). A Trial of Financial and Social Incentives to Increase Older Adults' Walking. *American Journal of Preventive Medicine*, *52*(5), e123–e130. doi: 10.1016/j.amepre.2016.11.011

⁵⁹ Finkelstein, E. A., Haaland, B. A., Bilger, M., Sahasranaman, A., Sloan, R. A., Nang, E. E. K., & Evenson, K. R. (2016). Effectiveness of activity trackers with and without incentives to increase physical activity (TRIPPA): a randomised controlled trial. *The Lancet Diabetes & Endocrinology*, *4*(12), 983–995. doi: 10.1016/S2213-8587(16)30284-4

- *Treatment*_j is a dummy variable taking value 0 for households allocated to the control group, and 1 for households allocated to *any* treatment group;
- γ_d is a fixed effect for the day of the week;
- *week*_{*ijd*} is a categorical variable for the (actual) calendar week that the read is recorded;
- baseline_{ijd} is the value of the outcome on the same day of the last week of the baseline period, approximately five months earlier. Missing values for baseline_{ijd} will be coded as -99 to ensure that we include as many participants as possible;

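### The 5-month physical-activity primary outcome is week 21 in the analysis sections but weeks 20-22 in Table 9 once mitigation is triggered, and nothing says which governs

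*Protocol*

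**What the plan says.** All references are to the protocol.

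- **Section 2.6.1.1, measurement time points:** the follow-up point is "the 21st week after randomisation for the 5m mark".
- **Section 2.6.3.2:** in the main specification, "we use 'valid' reads for all days of the 21st week (i.e. month 5) of the trial as outcomes". Invalid reads are replaced from the same weekday one week either side or, failing that, two weeks either side of the evaluation week. Footnote 56 works this through for one day of week 21. The 1- and 3-month analyses follow a similar process ("i.e. the 5th and 13th weeks respectively").
- **Section 2.6.3.5:** the primary outcomes are MVPA minutes and "steps at 5 months into the trial (week 21").
- **Table 9, 5-month row, default:** "we will use all valid daily PA data provided during the 21st week after randomisation for the 5m mark", with replacement from weeks 19-23.
- **Table 9, 5-month row, mitigation triggered:** every valid read of weeks 20, 21 and 22, with gaps filled "on the same day of the week within 2 adjacent weeks (i.e. weeks 18-24"). This sentence calls itself the 3-month mark, and the row is headed "5 month mark (starting the 20th week after randomisation").
- **Table 9, 3-month row:** week 13 by default, weeks 13-15 if triggered.
- **Table 2:** one row, marked as triggered, reads "Extend the data collection window from 2 to 3 weeks (21 days) at m3 and m5 for all measures". A separate row moves the month-5 window forward to week 20 and carries no trigger label.

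**The concern.** Sections 2.6.3.2 and 2.6.3.5 define the outcome, the replacement rule and the model. They contain no mitigation branch and do not refer to the one in Table 9. If mitigation is triggered, an analyst who follows section 2.6.3 departs from Table 9, and one who follows Table 9 departs from what section 2.6.3.2 calls the main specification. This affects two of the six primary outcomes. It also affects the 3-month results, which Table 2 makes the main assessment if the 5-month sample falls below 80% of 4,200 (0.80 x 4,200 = 3,360).

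There is a second, technical problem. The replacement rule assumes that the donor weeks lie outside the analysed week. In a three-week window the nearest donor weeks are often inside it, so one observed read could enter equation (1) more than once as if it were separate information.

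**Working it through.** **1. The plan's own figure.** Section 2.4.1 gives minimum detectable effects of 2.4 MVPA min/day and 371 steps/day. Inputs are 2,100 per side, SDs of 26 and 4,096, household ICC 0.3, baseline correlation 0.5, a mean of 0.39x1 + 0.41x2 + 0.20x3 = 1.81 adults per household, and Bonferroni for two outcomes (two-sided 0.05 assumed, so 0.025 each).

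Design effect = 1 + (1.81 - 1) x 0.3 = 1.243.

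Detectable effect in SD units = (2.241 + 0.842) x sqrt(2/2100 x 1.243 x (1 - 0.25)) = 0.0919. This gives 2.39 min/day and 376 steps/day, close to the stated values. The number of days per person does not enter, so the power calculation does not help decide which window was meant.

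**2. The two windows in days.** Week w covers days 7(w-1)+1 to 7w.

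| | Section 2.6.3 and Table 9 default | Table 9 triggered |
|---|---|---|
| Outcome weeks | 21 | 20, 21, 22 |
| Outcome days | 141-147 (7) | 134-154 (21) |
| Replacement reads drawn from | weeks 19-23 | weeks 18-24 |
| Maximum person-days at N = 4,200 | 29,400 | 88,200 |

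Of the 21 triggered days, 14 (67%) are outside week 21.

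**3. Precision.** With a within-person correlation r between days and complete wear, the variance of a k-day mean is proportional to r + (1 - r)/k. The ratio of standard errors, 21 days to 7, is sqrt[(r + (1-r)/21) / (r + (1-r)/7)].

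- r = 0.3: sqrt(0.333/0.400) = 0.913
- r = 0.4: sqrt(0.429/0.486) = 0.939
- r = 0.5: sqrt(0.524/0.571) = 0.957
- r = 0.6: sqrt(0.619/0.657) = 0.971

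The 21-day mean therefore has a standard error about 3-9% smaller. The values of r are assumed; the protocol gives none.

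**4. Re-used reads.** Take an invalid Monday in week 21 when the outcome window is weeks 20-22. The first-choice donors are the Mondays of weeks 20 and 22, and both are already outcome rows. An invalid Monday in week 20 draws on week 19 (outside) and week 21 (inside).

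I simulated weeks 18-24 with days valid independently with probability p, and applied the section 2.6.3.2 rule to each of weeks 20, 21 and 22. The table shows the share of analysed person-days that are filled, wholly or as part of an average, from a read that is itself an outcome row.

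| p | 0.97 | 0.9 | 0.7 | 0.5 | 0.3 |
|---|---|---|---|---|---|
| Share | 3% | 9% | 24% | 34% | 39% |

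The protocol states no valid-day probability. Its nearest figure, in section 2.6.3.2, is that fewer than 3% of historical users averaged under 6 hours of wear per day. That describes users' averages, not days.

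**The case against.** The best defence is that Table 9 prespecifies both branches and that a specific table overrides general text. By default it agrees with section 2.6.3, so the conflict arises only if mitigation is triggered. Equation (1) is indexed by day, with weekday and calendar-week terms, and accepts 21 days without change. Table 2's extension from two weeks to three may describe the collection period, since users are paid for syncing in weeks 21 and 22, and so need not contradict a one-week analysis window. The replacement rule could also be read as taking donors only from outside the whole three-week period, in which case nothing is re-used.

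Much of this stands. The override reading is weakened because the triggered sentence names the wrong time point, the row heading and its default text give different start weeks, and section 2.6.3 never refers to the branch. In Table 2 the numeric attrition threshold is footnoted to the payment rows, not to the window row. On replacement, the text supports either reading, and the week-by-week one is the more natural.

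A reader might go further and infer three things that the documents do not support.

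- **That the window could be picked by its result, inflating the type I error.** The trigger is operational and tied to attrition, and section 2.7.1 plans no interim outcome analysis. Nothing permits running both versions and keeping the better one.
- **That the analysed people would differ greatly.** Weeks 19-23 already supply replacements by default. A user whose last valid read is in week 18 looks like permanent drop-out, for which section 2.6.3.2 rules out replacement.
- **That the trigger is the expected scenario.** Where the protocol defines excessive attrition, it does so relative to the attrition already expected in Table 6.

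**Conclusion.** The contradiction is real but conditional. If mitigation is triggered, the protocol gives two definitions of the 5-month MVPA and steps outcomes and does not say which governs. The same holds at 3 months. The two versions differ in 14 of 21 days and, under the assumed correlations of 0.3-0.6 with complete wear, by 3-9% in standard error. The effect on the treatment estimate itself cannot be computed from the document.

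The re-use of reads depends on applying the replacement rule week by week. Its extent runs from about 3% to 39% of person-days across valid-day probabilities of 0.97 to 0.3, so it is small if wear is good and substantial if wear is sparse.

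**What to change.** In sections 2.6.3.2 (with footnote 56) and 2.6.3.5, state that if the window extension was triggered, the 5-month outcome is every valid daily read in weeks 20-22 (3-month: weeks 13-15), and otherwise week 21 (3-month: week 13). Say that the window is the same for all arms and is fixed before outcomes are analysed by arm.

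For the triggered case, use each read once. No day should be filled from a day that is itself in the outcome window, and any replacement should come only from outside it (5-month: weeks 18-19 and 23-24; 3-month: weeks 11-12 and 16-17).

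In Table 9's triggered 5-month text, change the 3-month label to 5-month. Align the start week across section 2.6.1.1, the Table 9 row heading and the Table 2 pull-forward row. Report week 21 alone as a sensitivity analysis.

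The cost is wording and one extra model run per physical-activity outcome. The downside is that some person-days stay unfilled and the triggered outcome averages over three weeks instead of one.
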